Likelihood methods, as well as single and multiple imputation methods will be implemented to account for the presence of missing data and to address occurrences of intercurrent events by ‘hypothetical’ strategies in the statistical analysis of the primary and secondary endpoints. For imputation-based methods, non-monotone missing data will be imputed based on a Markov Chain Monte Carlo method, assuming an underlying multi-variate normal distribution for continuous endpoints and the fully-conditional specification method for binary or ordinal endpoints. For imputation-based methods, monotone missing data will be imputed based on a monotone regression method for continuous endpoints and a fully-conditional specification logistic regression method for binary or ordinal endpoints. The variables used in the analysis model will be included in the imputation model. Here, the categorization into non-monotone and monotone missing data-patterns is based on all scheduled visits.

The ‘delta-adjusted’ pattern-mixture model provides a convenient framework for assessing the impact of departures from the missing at random (MAR) assumption in instances where the ‘control-based’ pattern-mixture model is not reasonable, e.g. when comparing 2 active treatments. For continuous endpoints, the ‘delta-adjusted’ pattern-mixture model assumes that within a given treatment arm, the mean response value among withdrawn subjects differs from the mean response among subjects remaining in the trial by a specified margin, denoted by Δ . For a given treatment arm at a specific timepoint, missing data are imputed based on the distribution of the conditional mean fitted to the observed data adjusted by the specified margin, Δ . When imputing missing ordinal data in the context of a logistic regression model, Δ is interpreted as the odds ratio of a given level on the logarithmic scale for withdrawals vs. completers.

THIS DOCUMENT CONTAINS CONFIDENTIAL INFORMATION AND MUST NOT BE COPIED OR MADE AVAILABLE TO ANY THIRD PARTY WITHOUT THE PRIOR WRITTEN CONSENT OF THE LEO PHARMA GROUP

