3. An ANCOVA model will be fitted to the PASI score at Week 1. This is to be done in the context of a proper imputation model as implemented in PROC MI using the monotone regression method. The model will include effects of baseline body weight (≤ 100 kg, > 100 kg), and baseline PASI score. The estimated parameters, and their variances, will be used to impute missing PASI scores at Week 1 in each of the 250 copies of the dataset generated above (seed=246673). Negative imputed values will be replaced by 0, and imputed values larger than 72 will be replaced by 72, thereby ensuring that imputed PASI scores are within the range from 0 to 72.
4. For each of the 250 copies of the dataset, missing PASI scores at Week 2 will be imputed in the same way as for Week 1. The imputations will be based on an ANCOVA model with the effects of baseline body weight (≤ 100 kg, > 100 kg) together with the PASI scores at baseline and Week 1. The estimated parameters, and their variances, will be used to impute missing values at Week 2 (the same seed=246673 will be used as in the previous step). Again, negative imputed values will be replaced by 0, and imputed values larger than 72 will be replaced by 72.
5. This stepwise procedure will then be repeated sequentially for Weeks 4, 6, 8, 10, 12, 14 and 16 with the modification that only the PASI scores from the 2 preceding visits will be included as covariates, in addition to the effect of baseline body weight (≤ 100 kg, > 100 kg).

The missing binary PASI 100 response at Week 16 will be derived from the corresponding underlying imputed PASI score. If the model does not converge, the baseline body weight variable will be dropped.

Impute treatment adherence status at Week 16

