2. An ordinal logistic regression model assuming proportional odds will be fitted to the IGA value at Week 1. This is to be done in the context of a proper imputation model as implemented in PROC MI using fully conditional specification logistic regression with the cumulative logit link function. The model will include effects of baseline body weight (≤ 100 kg, > 100 kg), and baseline IGA. The estimated parameters, and their variances, will be used to impute missing IGA values at Week 1 in each of the 250 copies of the dataset. The imputations will be done based on the predicted probabilities associated with each of the values on the IGA scale at Week 1.
3. For each of the 250 copies of the dataset, missing values at Week 2 will be imputed in the same way as for Week 1. The imputations will be based on a proportional odds logistic regression model with the effect of baseline body weight (≤ 100 kg, > 100 kg) together with the IGA values at baseline and Week 1. The estimated parameters, and their variances, will be used to impute missing values at Week 2.
4. This stepwise procedure will then be repeated sequentially for Weeks 4, 6, 8, 10, 12, 14, 16, 18, 20, 22, 24, 26, and 28 with the modification that only the IGA values from the 2 preceding visits will be included as covariates, in addition to the effect of baseline body weight (≤ 100 kg, > 100 kg).

THIS DOCUMENT CONTAINS CONFIDENTIAL INFORMATION AND MUST NOT BE COPIED OR MADE AVAILABLE TO ANY THIRD PARTY WITHOUT THE PRIOR WRITTEN CONSENT OF THE LEO PHARMA GROUP

The missing binary ‘having IGA of 0’ response at Week 16 will be derived from the corresponding underlying imputed IGA value.

Binary endpoints based on subject assessments

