5.4.1.1 Main analysis

For each of the 250 complete datasets, the treatment effect will be estimated, along with the associated standard error, from a logistic regression model, adjusted for baseline body weight (≤ 100 kg, > 100 kg) and the baseline value of the underlying response variable. Based on Rubin’s rules, a combined estimate and standard error for the treatment effect will be calculated and the associated t statistic will be used for testing the null hypothesis that the response rate for the brodalumab arm is less than or equal to the rate for the guselkumab arm, against the alternative that brodalumab is superior to guselkumab. The statistical test will be based on the odds ratio or, equivalently, on the log-odds ratio as expressed through the treatment coefficient in the logistic regression model. In practice, the t test will be carried out as a two-sided test at the 5% significance level, where the null hypothesis will only be rejected in favour of the stated alternative if the treatment effect estimate is in favour of brodalumab. This corresponds to a one-sided test at the 2.5% significance level.

To quantify the magnitude of the potential treatment effect, estimates of the LS-mean risk difference and odds ratio will be presented along with the associated 95% confidence intervals

THIS DOCUMENT CONTAINS CONFIDENTIAL INFORMATION AND MUST NOT BE COPIED OR MADE AVAILABLE TO ANY THIRD PARTY WITHOUT THE PRIOR WRITTEN CONSENT OF THE LEO PHARMA GROUP

(CIs), based on combining estimates and associated standard errors from the 250 analyses using Rubin's rules.

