5.4.3.1 Main analysis

Each of the 250 imputed datasets will be analysed based on an ANCOVA model, including baseline body weight (≤ 100 kg and > 100 kg), and treatment arm as factors and adjusting for the baseline value of the endpoint as a covariate. The pooled estimate of the difference in the LS-mean between the brodalumab and guselkumab arms, along with the associated 95% CIs and nominal p-values, will be presented based on applying Rubin’s rules to the estimates and standard errors from the aforementioned ANCOVA analyses of the imputed datasets.

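### From Week 4 the PASI and IGA imputation models leave out the baseline score, contrary to the SAP's own rule that analysis-model variables are included

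*SAP*

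**What the plan says.** The general rule in SAP 5.1 carries no exception: "The variables used in the analysis model will be included in the imputation model". Protocol 14.3.2 has the same sentence.

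The analysis models use baseline. The logistic model in SAP 5.4.1.1 adjusts for the body weight stratum "and the baseline value of the underlying response variable". The ANCOVA in SAP 5.4.3.1 has treatment and body weight as factors, "adjusting for the baseline value of the endpoint as a covariate".

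The imputation steps are in SAP 5.4.1. For PASI, the Week 1 model contains body weight and baseline PASI, and the Week 2 model contains body weight "together with the PASI scores at baseline and Week 1". After that: "This stepwise procedure will then be repeated sequentially for Weeks 4, 6, 8, 10, 12, 14 and 16", with the change that "only the PASI scores from the 2 preceding visits will be included as covariates", plus body weight. For IGA, the procedure runs on to Week 28 under the same limit: "only the IGA values from the 2 preceding visits will be included as covariates".

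Protocol 14.3.6.2 uses the same two-visit limit but starts it one step later. Its Week 4 model still has baseline and Week 2 PASI, and baseline leaves at Week 6. The SAP inserted a Week 1 step, which moved the loss of baseline to Week 4. Panel 22 in SAP Section 6 reports the added baseline and Week 1 steps but not this consequence.

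**The concern.** An imputation model that lacks a covariate of the analysis model imputes scores as if that covariate had no influence beyond the variables that are present. Here, imputed scores from Week 4 on are tied to baseline only through the two previous scores. If baseline still predicts the later score once those two are known, the association between baseline and outcome is weakened among the imputed subjects, and the analysis then adjusts for a variable that the imputation ignored.

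Also at stake is reproducibility, which the SAP sets as its own aim in the Introduction. A programmer who follows 5.1 and one who follows step 5 would build different models for the primary endpoint.

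**Working it through.** **1. Covariates side by side.** Treatment is represented because imputation is done within arm. Body weight is in every model. Baseline PASI is not:

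| PASI imputed at | Scores used, besides body weight | Baseline included |
|---|---|---|
| Week 1 | baseline | yes |
| Week 2 | baseline, Week 1 | yes |
| Week 4 | Weeks 1, 2 | no |
| Week 6 | Weeks 2, 4 | no |
| Weeks 8 to 14 | two preceding visits | no |
| Week 16 | Weeks 12, 14 | no |

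IGA follows the same pattern to Week 28. The Cox model for adherence in the same section does include baseline PASI.

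**2. Which values go through these models.** Intermittent PASI gaps go to the Markov chain step. That step truncates imputed baseline values, so baseline appears to be in it, although its variable list is not given. PASI step 5 therefore serves monotone gaps only. IGA has no such separate step: SAP Section 6 says full-data imputation is used, so every missing IGA value from Week 4 on is imputed without baseline.

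**3. Planned figures.** None changes. The protocol's power calculation uses Fisher's test on simulated responses and has no imputation model. As a check, with rate = λ01/(λ01+λ10) × (1 − exp(−16(λ01+λ10))), brodalumab gives 0.0333/0.0605 × (1 − exp(−0.968)) = 0.341 and guselkumab gives 0.0158/0.0593 × (1 − exp(−0.9488)) = 0.163. Exact Fisher power at 120 per arm is then 86.9%, against 87.0% in Protocol Panel 20.

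**4. Size for the Week 16 PASI = 0 rate.** The documents give no correlation structure and no missing-data rate for PASI, so all values here are assumptions. One arm of 200,000 subjects was simulated over the nine visits from Week 1 to Week 16. Each score was 0.45 × the previous score + 0.20 × the one before + d × baseline − 0.3 + normal noise (SD 1.5), held within 0 to 72. Scores were missing from Week 6 on, either unrelated to baseline or more often at high baseline, and were imputed with and without baseline. The rows with the largest overall shift for each d and missing-data range:

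| d | Missing | Rate with baseline | Rate without | Shift (points) |
|---|---|---|---|---|
| 0 | 22.8% | 38.11% | 38.19% | 0.08 |
| 0.05 | 13.2% | 22.99% | 23.21% | 0.22 |
| 0.10 | 13.1% | 11.93% | 12.12% | 0.19 |
| 0.05 | 22.8% | 21.87% | 22.40% | 0.53 |
| 0.10 | 23.1% | 11.67% | 11.94% | 0.27 |

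Within the high-baseline half the largest shifts were 15.15 − 14.50 = 0.65 points (13.2% missing) and 14.76 − 13.45 = 1.31 points (22.8% missing). These figures show how much the rate depends on the baseline term. They do not measure bias: both versions fall below the complete-data rate (23.99% in the second row), so the gap to complete data is not caused by leaving out baseline.

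**5. Size for the link with baseline.** Suppose all visits correlate equally, with correlation r. A last visit imputed from two observed preceding visits then has correlation 2r²/(1+r) with baseline. For r = 0.3 this is 0.18/1.3 = 0.138, and for r = 0.5 it is 0.5/1.5 = 0.333. With 15% missing completely at random, the correlation over all subjects is 0.85 × 0.30 + 0.15 × 0.138 = 0.28 and 0.85 × 0.50 + 0.15 × 0.333 = 0.475, against 0.30 and 0.50.

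**6. Where baseline leaves the window for other scores.** By the schedule in Protocol Section 4, DLQI is collected at baseline and every 4 weeks from Week 4, so a two-visit window loses baseline from Week 12. SF-36v2 is collected at baseline and Weeks 4, 8, 16 and 28, so it loses baseline from Week 16.

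**The case against.** The best defence is that almost no primary-endpoint value should reach step 5. SAP Section 6 reports that the blind review found no event time censored other than administratively. Since SAP 5.4.2.1 lists withdrawal and pandemic-related discontinuation as the other censoring causes, neither occurred before a first PASI 100 or a non-pandemic discontinuation. A subject in the latter group before Week 16 counts as a non-responder whatever the PASI. PASI 100 means PASI = 0, so deriving it needs no baseline. The two-visit limit is worded as a deliberate modification in both documents, so the sentence in 5.1 may simply be too broad. And if dependence fades with time, so that baseline adds nothing given the last two scores, nothing is lost. The equal-correlation model in step 5 of the working is the kind of structure that makes the loss large.

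Most of this stands, and it fixes the size of the point for the primary endpoint. It does not remove the conflict in the text. The blind-review statement concerns event times and does not show that PASI, IGA or patient-reported scores are complete. Under the treatment-policy strategies (continuous endpoints and the first supplementary estimand), a subject who stops IMP and later leaves has scores that these models must supply. The delta-adjusted analysis for prohibited medication deletes observed scores and imputes them again.

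**Conclusion.** The conflict is clear on the text: 5.1 requires the baseline value in the imputation models, and 5.4.1 leaves it out from Week 4 for both PASI and IGA, with no reason given. The consequence is minor. For the primary treatment estimate the expected effect is nil if baseline adds nothing given the last two scores. Under the assumed direct effects, the overall PASI = 0 rate in one arm moves by at most about 0.2 points at 5 to 13% missing and about 0.5 points at 20 to 23%. The treatment difference moves only by the difference between the two arms' shifts. The practical gain is for IGA, the treatment-policy estimands, endpoints defined relative to baseline, and the sensitivity analyses.

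A reader might infer two stronger things that the documents do not support. The first is that a biased baseline coefficient harms the primary test. That coefficient is a nuisance parameter, inference is on treatment, and imputation within arm keeps treatment fully represented. The second is that imputed PASI 90 status would be inconsistent with baseline severity. PASI 90 is calculated from the imputed score and the subject's own baseline, so it is consistent by construction; at most an association is weakened.

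**What to change.** In SAP 5.4.1, PASI step 5 and IGA step 4, state that each model contains the baseline value of the score, the scores at the two most recent earlier visits, and the body weight stratum. Apply the same to the other scores wherever the two-visit window no longer contains baseline (for example DLQI from Week 12 and SF-36v2 from Week 16). If the sponsor prefers the present models, the alternative is to qualify the sentence in 5.1 and justify the omission in Section 6.

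The cost is a few words and one covariate, already collected, in each within-arm model. The non-convergence fallback should be checked at the same time. For PASI it drops only body weight, and none is stated separately for the ordinal IGA models, where an extra covariate is most likely to cause trouble. The change should be made before unblinding.

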5.4.1.1 Main analysis

For each of the 250 complete datasets, the treatment effect will be estimated, along with the associated standard error, from a logistic regression model, adjusted for baseline body weight (≤ 100 kg, > 100 kg) and the baseline value of the underlying response variable. Based on Rubin’s rules, a combined estimate and standard error for the treatment effect will be calculated and the associated t statistic will be used for testing the null hypothesis that the response rate for the brodalumab arm is less than or equal to the rate for the guselkumab arm, against the alternative that brodalumab is superior to guselkumab. The statistical test will be based on the odds ratio or, equivalently, on the log-odds ratio as expressed through the treatment coefficient in the logistic regression model. In practice, the t test will be carried out as a two-sided test at the 5% significance level, where the null hypothesis will only be rejected in favour of the stated alternative if the treatment effect estimate is in favour of brodalumab. This corresponds to a one-sided test at the 2.5% significance level.

To quantify the magnitude of the potential treatment effect, estimates of the LS-mean risk difference and odds ratio will be presented along with the associated 95% confidence intervals

THIS DOCUMENT CONTAINS CONFIDENTIAL INFORMATION AND MUST NOT BE COPIED OR MADE AVAILABLE TO ANY THIRD PARTY WITHOUT THE PRIOR WRITTEN CONSENT OF THE LEO PHARMA GROUP

(CIs), based on combining estimates and associated standard errors from the 250 analyses using Rubin's rules.

5.4.1.2 Sensitivity analyses

The following sensitivity analyses will be conducted based on the logistic regression model specified for the main analysis.

5.4.1.2.1 Robustness with respect to MAR assumption

These sensitivity analyses will assess the robustness of the results of the main analysis with respect to the MAR assumption. For subjects experiencing intercurrent events to be addressed by 'composite' or 'hypothetical' strategies, cf. [Panel 11](#), the data observed after the occurrence of such events will be excluded from the imputation models for the following sensitivity analyses. Missing data will be imputed in separate sensitivity analyses based on each of the following imputation algorithms:

- Non-responder imputation.
- 'Delta-adjusted' pattern-mixture model.

The sensitivity analysis based on non-responder imputation will be done from the same multiply-imputed datasets as were used for the main analysis with the following modification. All binary response values that were originally imputed for missing data that did not arise after the occurrence of intercurrent events to be addressed by 'composite' or 'hypothetical' strategies, will instead be imputed as non-responses.

For sensitivity analyses based on 'delta-adjusted' pattern-mixture models, multiply-imputed datasets will be generated just as for the main analysis (including the use of the same seeds) with the following modification. After having obtained 250 copies of the dataset with a monotone missing data pattern, imputed scores will be adjusted by a specified margin Δ for those remaining missing scores, which did not arise after the occurrence of intercurrent events specified to be addressed by 'composite' or 'hypothetical' strategies. The adjustment by Δ will be applied subsequently at each visit up to the end of the trial, in addition to using previously Δ -adjusted values as predictors. The same margin Δ will be used for both treatment groups. [Panel 13](#) specifies the margins to be used.

THIS DOCUMENT CONTAINS CONFIDENTIAL INFORMATION AND MUST NOT BE COPIED OR MADE AVAILABLE TO ANY THIRD PARTY WITHOUT THE PRIOR WRITTEN CONSENT OF THE LEO PHARMA GROUP

Panel 13. Margins to be used for adjustment in ‘delta-adjusted’ pattern mixture models

Type of score	Score	Interpretation of Δ	Margin Δ					
Continuous	PASI	Shift in score	-4.5	-3.0	-1.5	+1.5	+3.0	+4.5
Continuous	PP-PASI	Shift in score	-18	-12	-6	+6	+12	+18
Continuous	DLQI total score	Shift in score	-4.5	-3.0	-1.5	+1.5	+3.0	+4.5
Continuous	SF-36v2 PCS	Shift in score	-18	-12	-6	+6	+12	+18
Continuous	SF-36v2 MCS	Shift in score	-18	-12	-6	+6	+12	+18
Continuous	Pruritus NRS (weekly average)	Shift in score	-0.36	-0.24	-0.12	+0.12	+0.24	+0.36
Continuous	Pain NRS (weekly average)	Shift in score	-0.36	-0.24	-0.12	+0.12	+0.24	+0.36
Ordinal	IGA	Shift in log-odds for IGA = 0	-0.09	-0.07	-0.05	+0.05	+0.07	+0.09
Ordinal	PP-IGA	Shift in log-odds for PP-IGA = 0	-0.35	-0.27	-0.17	+0.17	+0.27	+0.35
Ordinal	sPGA-G	Shift in log-odds for sPGA-G = 0	-0.35	-0.27	-0.17	+0.17	+0.27	+0.35

Abbreviations: DLQI = Dermatology Life Quality Index; IGA = Investigator’s Global Assessment; MCS = mental component summary; NRS = numeric rating scale; PASI = Psoriasis Area and Severity Index; PCS = physical component summary; sPGA = static Physician’s Global Assessment; PP-IGA = palmoplantar IGA; PP-PASI = palmoplantar PASI; SF-36v2 = 36-item Short Form Health Survey version 2, acute recall; sPGA-G = sPGA of genitalia.

With m denoting the number of post-baseline assessments scheduled to be performed per subject for a given score, the margins Δ in [Panel 13](#) generally approximate multiples

$$-1/m, -2/(3m), -1/(3m), 1/(3m), 2/(3m), \text{ and } 1/m$$

of the scoring range for continuous scores, and log(odds ratios) corresponding to the odds ratios

$$\sqrt[m]{1/4}, \sqrt[m]{1/3}, \sqrt[m]{1/2}, \sqrt[m]{2}, \sqrt[m]{3}, \sqrt[m]{4}$$

THIS DOCUMENT CONTAINS CONFIDENTIAL INFORMATION AND MUST NOT BE COPIED OR MADE AVAILABLE TO ANY THIRD PARTY WITHOUT THE PRIOR WRITTEN CONSENT OF THE LEO PHARMA GROUP

for ordinal scores. The reason for considering m in the above specifications is that the potential difference emerging between subsequent assessments for withdrawals vs. completers may be expected to be larger when the subsequent assessments are further distanced in time.

5.4.1.2.2 Robustness with respect to assumption that treatment effect does not depend on baseline body weight stratum

This sensitivity analysis will assess the robustness of the results of the main analysis with respect to the assumption that the effect of treatment does not depend on baseline body weight. To carry out this sensitivity analysis, an interaction term between baseline body weight (≤ 100 kg, > 100 kg) and treatment arm will be included in the logistic regression model described in the main analysis.

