5.3 Trial rationale

With increasing availability of novel biologics with new targets, the complexity of choosing the appropriate biologic treatment is ever more challenging for physicians. This applies not only to choosing the most efficacious treatment for the patient, but also to deciding on subsequent treatment options if the patient has inadequate response to a biologic treatment.

Ustekinumab modulates proinflammatory signalling through the inhibition of IL-12 and IL-23. Several trials evaluating efficacy of more modern biologic treatments have demonstrated superiority of the newer agents (targeting IL-17A, IL-23p19, or IL-17RA) over ustekinumab (6-11).

The efficacy of brodalumab for the treatment of psoriasis has been confirmed in 3 placebo-controlled phase 3 trials, 2 of which included an ustekinumab comparator arm (AMAGINE-2 and -3). A subanalysis of these trials showed that rescue treatment with brodalumab improved skin outcomes among subjects with inadequate response to ustekinumab (9, 10, 12).

The head-to-head trial of guselkumab versus ustekinumab in subjects inadequately treated with ustekinumab (NAVIGATE trial) has demonstrated increased psoriasis improvement in subjects randomised to guselkumab compared with those randomised to continue on ustekinumab (4).

By comparing data from the AMAGINE and the NAVIGATE trials, it was concluded that brodalumab treatment would lead to significantly higher PASI 100 rates than guselkumab treatment after 16 weeks of treatment (34.7% vs. approximately 18%, respectively) (4, 12). No trials have, however, directly compared IL-17RA antagonism with IL-23p19 inhibition.

THIS DOCUMENT CONTAINS CONFIDENTIAL INFORMATION AND MUST NOT BE COPIED OR MADE AVAILABLE TO ANY THIRD PARTY WITHOUT THE PRIOR WRITTEN CONSENT OF THE LEO PHARMA GROUP

Therefore, the primary objective of this trial is to compare the efficacy of brodalumab versus guselkumab in adult subjects with moderate-to-severe plaque psoriasis and inadequate response to ustekinumab, thereby providing results that could support decision-making in the clinical setting.

The primary endpoint is PASI 100 at Week 16. PASI 100 is chosen due to substantial evidence highlighting the importance of complete clearance from the patient's perspective, improving quality of life and decreasing the disease burden (13). Moreover, PASI 100 allows better and most accurate differentiation between highly efficacious treatments available for the treatment of psoriasis today.

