7.2 Number of subjects needed

This trial will be conducted at approximately 75 sites in Europe.

Assuming a screening failure of 18%, approximately 293 subjects will be screened, and 240 eligible subjects will be randomised in a 1:1 ratio to treatment with either brodalumab or guselkumab. Randomisation will be stratified by body weight (≤ 100 kg, > 100 kg).

The statistical power considerations for this sample size are described in Section 14.1.

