Panel 20 provides the estimated marginal power for the primary and key secondary endpoints and the conjunctive power for rejecting the null hypotheses associated with the primary and key secondary endpoints, while controlling the familywise error rate (FWER) at the 5% significance level (for 2-sided Fisher's Exact and Gray's tests). The power analysis is based on 100,000 simulations, from the alternating two-state model illustrated in Panel 18, assuming the underlying transition intensities for the brodalumab arm were,

- e) $\lambda_{broda,0,1} = 1.00 \cdot \hat{\lambda}_{broda,0,1} = 0.0333$ and $\lambda_{broda,1,0} = 1.00 \cdot \hat{\lambda}_{broda,1,0} = 0.0272$,
- l) $\lambda_{broda,0,1} = 0.98 \cdot \hat{\lambda}_{broda,0,1} = 0.0326$ and $\lambda_{broda,1,0} = 1.02 \cdot \hat{\lambda}_{broda,1,0} = 0.0277$ or
- u) $\lambda_{broda,0,1} = 1.02 \cdot \hat{\lambda}_{broda,0,1} = 0.0340$ and $\lambda_{broda,1,0} = 0.98 \cdot \hat{\lambda}_{broda,1,0} = 0.0266$,

and assuming the underlying transition intensities for the guselkumab arm were

- e') $\lambda_{gus,0,1} = 1.00 \cdot \hat{\lambda}_{gus,0,1} = 0.0158$ and $\lambda_{gus,1,0} = 1.00 \cdot \hat{\lambda}_{gus,1,0} = 0.0435$,
- l') $\lambda_{gus,0,1} = 0.98 \cdot \hat{\lambda}_{gus,0,1} = 0.0155$ and $\lambda_{gus,1,0} = 1.02 \cdot \hat{\lambda}_{gus,1,0} = 0.0444$ or
- u') $\lambda_{gus,0,1} = 1.02 \cdot \hat{\lambda}_{gus,0,1} = 0.0162$ and $\lambda_{gus,1,0} = 0.98 \cdot \hat{\lambda}_{gus,1,0} = 0.0427$.

THIS DOCUMENT CONTAINS CONFIDENTIAL INFORMATION AND MUST NOT BE COPIED OR MADE AVAILABLE TO ANY THIRD PARTY WITHOUT THE PRIOR WRITTEN CONSENT OF THE LEO PHARMA GROUP

The scenarios described in bullet points l), u), l') and u') have been introduced for robustness of the resulting sample size with respect to small perturbations of the transition intensities.

Panel 20: Estimated conjunctive power for rejecting the hypotheses associated with the primary and key secondary endpoints

Sample size per arm	Scenario for transition intensities				Power for the primary endpoint	Power for the key secondary endpoint	Conjunctive power		
	$\lambda_{\text{broda},0,1}$	$\lambda_{\text{broda},1,0}$	$\lambda_{\text{gus},0,1}$	$\lambda_{\text{gus},1,0}$					
N=110	e)	0.0333	0.0272	e')	0.0158	0.0435	83.3%	96.8%	82.5%
N=110	e)	0.0333	0.0272	l')	0.0155	0.0444	85.3%	97.4%	84.6%
N=110	e)	0.0333	0.0272	u')	0.0162	0.0427	80.9%	95.8%	79.9%
N=110	l)	0.0326	0.0277	e')	0.0158	0.0435	80.7%	95.8%	79.7%

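### The delta-adjusted analysis uses one margin for both arms, on a PASI 100 grid too coarse and an IGA grid too narrow to locate a tipping point; an arm-specific grid would be a cheap improvement

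*SAP*

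**What the plan says.** The primary endpoint is PASI 100 at Week 16, tested for brodalumab superiority (SAP 5.4.1.1): "In practice, the t test will be carried out as a two-sided test at the 5% significance level", with rejection only if the estimate favours brodalumab.

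SAP 5.4.1.2.1 plans two checks of the MAR assumption: non-responder imputation and delta-adjusted pattern-mixture models. For the latter:

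- "The same margin Δ will be used for both treatment groups".
- "The adjustment by Δ will be applied subsequently at each visit up to the end of the trial", with already shifted values used as predictors.
- Panel 13 fixes six margins per score. For PASI they are ±1.5, ±3.0 and ±4.5 points. For IGA they are ±0.05, ±0.07 and ±0.09, read as "Shift in log-odds for IGA = 0".
- The margins approximate 1/3, 2/3 and 3/3 of the score range divided by m (continuous scores), or the m-th roots of odds ratios 2, 3 and 4 and their inverses (ordinal scores). Here m is the number of scheduled post-baseline assessments.

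Δ applies only to scores still missing after the monotone step that do not follow an intercurrent event handled by a composite or hypothetical strategy. SAP 5.5.1.2 uses the same methods for the first supplementary estimand. Panel 22 drops the retrieved-data model that the protocol had listed there.

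**The concern.** A sensitivity analysis for a superiority claim should include the departure that would undo the claim: missing brodalumab subjects faring worse than MAR predicts, and missing guselkumab subjects faring the same or better. A common Δ moves both arms the same way, and so does non-responder imputation. The protocol does not require this. Its Section 14.3.2 defines Δ within a given treatment arm and offers the method for comparing two active treatments.

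The step sizes add to the problem. Response means PASI exactly 0, so whole-point shifts repeated at each missed visit push a missing subject quickly to one side of the threshold. The IGA shifts are fractions of an odds ratio spread over 15 visits. Six margins per endpoint look like a graded stress test, but for PASI 100 and IGA they give few informative intermediate points.

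**Working it through.** **Reproducing the plan's figure.** Protocol 14.1 states: "The power analysis is based on 100,000 simulations, from the alternating two-state model illustrated in Panel 18". Scenario e/e' has intensities 0.0333/0.0272 for brodalumab and 0.0158/0.0435 for guselkumab.

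π(16) = λ01/(λ01+λ10) × [1 − exp(−16(λ01+λ10))]

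- Brodalumab: 0.5504 × 0.6202 = 34.1%.
- Guselkumab: 0.2664 × 0.6128 = 16.3%.

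The protocol's source rates are "34.7% vs. approximately 18%, respectively". Exact enumeration of the two-sided 5% Fisher test at 120 per arm gives 86.9% power, against 87.0% in Panel 20. These rates are used below.

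**Reproducing the margins.** Visits at Weeks 1, 2 and then every 2 weeks to Week 28 give m = 15.

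- PASI: 72/15 × (1/3, 2/3, 1) = 1.6, 3.2, 4.8. The SAP has 1.5, 3.0, 4.5 and calls the margins approximate.
- IGA: ln(2, 3, 4)/15 = 0.046, 0.073, 0.092. The SAP has 0.05, 0.07, 0.09.

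**Common against opposite shifts.** The planned size is "240 eligible subjects will be randomised in a 1:1 ratio", so 120 per arm. The number missing, k per arm, is assumed, with m' = k/120. Observed subjects respond at the planning rates.

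- Both arms at the same limit: difference = (1 − m')(p1 − p2).
- Brodalumab all non-response, guselkumab all response: difference = (1 − m')(p1 − p2) − m'.

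The p-values are two-sided, from a pooled z test on expected rates, as an approximation to the planned logistic model.

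| Missing per arm | Both non-response | Both response | Opposite limits |
|---|---|---|---|
| 0 | 17.8 points, p = 0.0015 | same | same |
| 6 (5%) | 16.9, p = 0.002 | 16.9, p = 0.004 | 11.9, p = 0.036 |
| 7 (5.8%) | 16.8, p = 0.002 | 16.8, p = 0.004 | 10.9, p = 0.056 |
| 12 (10%) | 16.0, p = 0.003 | 16.0, p = 0.008 | 6.0, p = 0.30 |

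**PASI 100 steps.** If Δ is added after truncation at 0, a positive margin gives no responders by construction. If it is added before, simulated stepwise imputation gives between 0% and about 3%. The simulation assumed baseline means of 6, 10 and 18, and 7% to 19% response under MAR. The negative side depends on the length of the gap:

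| Δ | 4 or more visits missed | Only Week 16 imputed |
|---|---|---|
| −4.5 | 100% response | 59–100% |
| −3.0 | 97–100% | 43–98% |
| −1.5 | 61–100% | 27–78% |

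**IGA steps.** At one visit, ±0.09 moves 30% to 28.1% or 31.9%, and 50% to 47.8% or 52.2%; the largest move is about 2.3 points. Week 16 is the 9th post-baseline visit and the full analysis set requires one post-baseline PASI, so about 8 visits can be missing. With full carry-over the odds ratio is exp(8 × 0.09) = 2.05. For four missed visits it is exp(0.36) = 1.43, which moves 30% to 23% or 38%.

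**The case against.** The strongest counter-argument is that little is in scope for the primary estimand. Discontinuation of IMP independent of the pandemic already counts as non-response, and pandemic-related discontinuation has its own hypothetical imputation. A subject who misses Week 16 but has later PASI data is intermittently missing and receives no Δ. A subject who withdraws before any PASI 100, with no IMP discontinuation counted as an intercurrent event, would be right-censored under SAP 5.4.2.1, and Panel 22 reports that the blind review found only administrative censoring. This stands and limits the practical weight. It does not exclude subjects lost after an earlier PASI 100, or trial completers with no PASI from Week 16 on. Nor does it cover the first supplementary estimand, where withdrawals after IMP discontinuation are in scope.

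A reader might infer that a common Δ cannot show whether missing data overturn the result. The documents do not support that. A common Δ does test equal departures, and it can tip the result when missingness is unbalanced: with 0 brodalumab and 12 guselkumab subjects missing, all counted as responders, p = 0.11.

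A reader might also call the PASI margins all-or-none. That is too strong when one visit is imputed, as the table shows. It does not apply to absolute PASI as a continuous endpoint.

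Finally, the common margin is disclosed and pre-specified, IGA is outside the testing hierarchy, and nothing in the documents suggests that missing brodalumab subjects fare worse. The opposite-limits case is a bound, not a forecast. All of this is fair. It argues for reporting where the result tips, not for leaving that direction untested.

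**Conclusion.** This is a cheap improvement, not a flaw in the main analysis. The planned runs examine equal departures from MAR only, unless missingness differs between arms. For PASI 100, three of the six margins add almost nothing to non-responder imputation, and after several consecutive missed visits the others make most or nearly all missing subjects responders. The IGA margins reach an odds ratio of at most about 2 at Week 16, even with full carry-over.

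At the planning rates and 120 per arm, about 7 missing subjects per arm could remove significance at opposite limits, while the common limits stay at 0.002 to 0.004. This rests on balanced missingness and the planned sample size. The trial ended early, and neither the actual size nor the number missing is given. The PASI percentages also depend on assumed trajectories.

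It would go too far to conclude that a fragile primary result would pass unnoticed: the documents suggest few values in scope there. The clearer gain is for the first supplementary estimand.

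**What to change.** For PASI 100 at Week 16, under the primary and first supplementary estimands, add an arm-specific two-way grid or a tipping-point analysis. Apply the shift once, at the analysis visit, on the log-odds of response. One workable set per arm is 0, ±log 2, ±log 4 and the all-non-response and all-response limits: 7 × 7 = 49 cells. Include the corner with brodalumab worse and guselkumab better, and report where significance is lost.

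For IGA, replace the per-visit m-th-root margins with the same response-scale shift. This also settles where Δ enters: SAP 5.4.1.2.1 places it after a monotone step, which the IGA imputation no longer has.

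The cost is more sensitivity runs and a revised Panel 13. The main analysis is unchanged.
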